8.4.2. Tertiary Endpoint Analyses

The tertiary endpoints will be summarized descriptively.

Summary statistics will be provided for the continuous endpoints (eg, total MD-ADL score, total QMG score, levels of total IgG and subtypes, anti-AChR/anti-MuSK antibodies) in terms of absolute values, changes from TP₁B or changes from TP_nB, by cycle and available time points. For levels of total IgG and subtypes and also anti-AChR/anti-MuSK antibodies, the percentage change from TP₁B and from TP_nB will also be presented.

Frequency tables will be made for incidence and prevalence of ADA to efgartigimod.

8.5. Interim Analyses

Interim analyses might be performed to support questions for authorities and/or submissions.

9. QUALITY CONTROL AND QUALITY ASSURANCE

9.1. Investigator's Responsibility

The investigator will comply with the protocol (which has been approved/given favorable opinion by the Ethics Committee), ICH GCP, and applicable regulatory requirements. The investigator is ultimately responsible for the conduct of all aspects of the trial at the trial site and verifies by signature the integrity of all data transmitted to the sponsor. The term “investigator” as used in this protocol as well as in other trial documents, refers to the investigator or authorized trial personnel that the investigator has designated to perform certain duties. Sub-investigators or other authorized trial personnel are eligible to sign for the investigator, except where the investigator's signature is specifically required.

9.2. Quality Control of Data

Quality control will be applied to each stage of data handling.

The following steps will be taken to ensure the accuracy, consistency, completeness, and reliability of the data:

- Investigator meetings
- Central laboratories for clinical laboratory parameters and ECGs
- Site initiation visit
- Routine site monitoring
- Ongoing site communication and training
- Ongoing oversight by Clinical Trial Monitors of safety parameters and adherence to selection criteria
- Data management quality control checks
- Continuous data acquisition and cleaning
- Quality control check of the CTR
- To avoid inter-observer variability, every effort should be made to ensure that the same individual who made the initial baseline determinations completes all safety and disease severity evaluations.

In addition, sponsor and/or sponsor's designated CRO Clinical Quality Assurance (CQA) Department may conduct periodic audits of the trial processes, including, but not limited to trial site, or site visits, central laboratories, vendors, clinical database, and final CTR. When audits are conducted, access must be authorized for all trial-related documents including medical history and concomitant medication documentation to authorized sponsor's representatives and regulatory authorities.

9.3. Monitoring

The sponsor has engaged the services of a CRO to perform all clinical trial monitoring functions within this clinical trial. Sponsor's designated CRO monitors will work in accordance with SOPs of the CRO.

Monitoring visits must be conducted according to the applicable ICH GCP guidelines to verify that, among others, the:

- Data are authentic, accurate, and complete.
- Safety and rights of patients are being protected.
- Trial is conducted in accordance with the currently approved protocol, any other trial agreements and all applicable regulatory requirements.

The investigator and the head of the medical institution (where applicable) agrees to allow the Clinical Trial Monitor direct access to all relevant documents.

The investigator must ensure provision of reasonable time, space and qualified personnel for monitoring visits.

The Clinical Trial Monitor will perform an eCRF review and Source Document Verification (SDV).

The Source Documentation Agreement Form describes the source data for the different data in the eCRF. This document should be completed and signed by the Clinical Trial Monitor and investigator and should be filed in the investigator's trial file. Any data item for which the eCRF will serve as the source must be identified, agreed and documented in the Source Documentation Agreement Form.

Upon completion or premature discontinuation from the trial, the Clinical Trial Monitor will conduct site closure activities with the investigator and site staff as appropriate, in accordance with applicable regulations, ICH GCP guidelines and CRO/sponsor procedures.

Monitoring details describing strategy (eg, risk-based initiatives in operations and quality such as Risk Management and Mitigation Strategies and Analytical Risk-Based Monitoring), methods, responsibilities and requirements, including handling of noncompliance issues and monitoring techniques (central, remote, or on-site monitoring) are provided in the monitoring plan.

9.4. Data Management

Data generated within this clinical trial will be handled according to the SOPs of the Data Management and Biostatistics departments of the sponsor's designated CRO.

Case report forms are provided for each patient in electronic format. It will be transcribed by the trial site staff from the source documents onto the eCRF. Date must be entered in English and guidelines for eCRF completion, including the collection of investigator's e-signature, will be provided by the CRO. Appropriate training and security measures will be completed with the investigator and all authorized trial site staff prior to the trial being initiated and any data being entered into the system for any trial patient at the site.

The eCRF is essentially considered a data entry form and should not constitute the original (or source) medical records unless otherwise specified. Source documents are all documents used by the investigator or hospital that relate to the patient's medical history, that verify the existence of the patient, the inclusion and exclusion criteria, and all records covering the patient's participation in the trial. They can include laboratory notes, ECG results, memoranda, pharmacy dispensing records, patient files, etc. The eCRFs should be completed by the investigator or a qualified designee from the site as soon as the data are available.

As a matter of regulation, the investigator is responsible for the accuracy and authenticity of all clinical data entered onto eCRFs. Prior to database lock, each completed eCRF must be reviewed for accuracy by the investigator, corrected as necessary and then approved. The investigator's e-signature serves to attest that the information contained on the eCRFs has been reviewed by the investigator and is true and accurate. The investigator will be required to electronically sign off the eCRF.

The data will be verified for missing data, inconsistencies, and for necessary medical clarifications. Queries arising from these checks will be flagged to the trial site, and the trial site staff will correct data, confirm or clarify data as appropriate. The CRO will provide the details of the review process in a data management plan and monitoring plan. Any change, including the issuing of queries, will be fully audit trailed by the EDC application, meaning the name of the person, time, and date stamp are recorded, as well as the reason for change.

Data will also be provided by third party vendors, such as the results generated by the central labs, the Interactive Response Technology (IRT) provider, or centralized ECG reading. These data will need to be reconciled with the data recorded in the eCRF before it can be merged with the eCRF data into the clinical database. The CRO will provide a data management plan detailing this reconciliation.

Adverse events, concomitant diseases/medical history terms will be assigned to a lowest level term (LLT) and a preferred term (PT) and will be classified by high level term (HLT), high level group term, and primary system organ class (SOC) according to the Medical Dictionary for Regulatory Activities (MedDRA) thesaurus.

Prior and concomitant medications will be classified according to active drug substance using the World Health Organization Drug Dictionary (WHO-DD). The generic name, the preferred name, and the WHO name will be assigned using WHO-DD thesaurus.

The Anatomical Therapeutic Chemical (ATC) classes will be assigned to the prior and concomitant medications.

9.5. Quality Assurance Audit

Trial sites, the trial database and trial documentation may be subject to Quality Assurance audit during the course of the trial by the sponsor or sponsor's designee (CRO or other vendor) on behalf of sponsor. In addition, inspections may be conducted by regulatory bodies at their discretion.

10. ETHICS

10.1. Institutional Review Board or Independent Ethics Committee

The investigator will provide the sponsor or designee with documentation of IRB/IEC approval of the protocol and informed consent documents before the trial may begin at the trial sites. The investigator will supply documentation to the sponsor or designee of the required IRB/IEC's annual renewal of the protocol, and any approvals of revisions to the informed consent document or amendments to the protocol.

The investigator will report promptly to the IRB/IEC, any new information that may adversely affect the safety of patients or the conduct of the trial. Similarly, the investigator will submit written summaries of the trial status to the IRB/IEC annually, or more frequently if requested by the IRB/IEC. Upon completion of the trial, the investigator will provide the IRB/IEC with a brief report of the outcome of the trial, if required.

10.2. Ethical Conduct of the Trial

This trial will be conducted, and the informed consent will be obtained, according to the ethical principles stated in the Declaration of Helsinki (2013), the applicable guidelines for GCP, or the applicable drug and data protection laws and regulations of the countries where the trial will be conducted.

To comply with the Declaration of Helsinki (2013), argenx is assessing the appropriateness and possibility of making the study drug available for clinical study participants post-trial.

10.3. Patient Information and Informed Consent

The ICF, will be used to explain the risks and benefits of trial participation to the patient in simple terms before the patient rolled over into the trial. A separate ICF will be given in case of pregnancy of a female partner of male patient. The ICF contains a statement that the consent is freely given, that the patient is aware of the risks and benefits of entering the trial, and that the patient is free to withdraw from the trial at any time. Written consent must be given by the patient and/or legally acceptable representative, after the receipt of detailed information on the trial.

All ICFs must be available in the local and vernacular languages required at the site and include patient information sheets/brochures that outline the trial procedures. All ICF(s) must be signed and dated by the patient or a legally acceptable representative.

For patients who are unable to read and write, the patient information sheet and ICF(s) should be read to the patient in his/her native language in the presence of a legally acceptable representative who is literate and not affiliated with the trial. The patient having understood the information given to him/her in the presence of a legally acceptable representative will thumbprint the ICF(s) and the same will be countersigned by the legally acceptable representative. If the patient or legally acceptable representative cannot read, then an impartial witness will witness and attest the entire consent process and will be required to sign the ICF.

Confirmation of a patient's informed consent must also be documented in the patient's medical record prior to any testing under this protocol, including SEB tests and assessments.

The investigator is responsible for ensuring that informed consent is obtained from each patient or legally acceptable representative and for obtaining the appropriate signatures and dates on the informed consent document prior to the performance of any protocol procedures and prior to the administration of efgartigimod. The investigator will provide each patient with a copy of the signed and dated ICF(s).

10.4. Patient Data Protection

The ICF will incorporate (or, in some cases, be accompanied by a separate document incorporating) wording that complies with relevant data protection and privacy legislation.

11. TRIAL ADMINISTRATION

11.1. Data Handling and Record Keeping

It is the investigator's responsibility to maintain essential trial documents (including records and documents pertaining to the conduct of this trial and the distribution of IMP, regulatory documents, eCRFs, signed patient ICFs, laboratory test results, IMP inventory records, source documents, relevant correspondence, AE reports, and all other supporting documentation) as required by the applicable national regulatory requirements. The trial site should plan on retaining such documents for approximately 25 years after trial completion. The trial site should retain such documents until at least 2 years after the last approval of a marketing application in an ICH region and until there are no pending or contemplated marketing applications in an ICH region or at least 2 years after the formal discontinuation of clinical development of efgartigimod. The sponsor will notify the principal investigator of these events.

These documents should be retained for a longer period if required by the applicable regulatory requirements or the hospital, institution, or private practice in which the trial is being conducted. Patient identification codes (patient names and corresponding trial numbers) will be retained for this same period of time. These documents may be transferred to another responsible party, acceptable to sponsor, who agrees to abide by the retention policies. The investigator is required to notify the sponsor (or an authorized representative) in writing prior to changing the location or status of any essential clinical trial documents. The investigator must contact sponsor prior to disposing of any trial records.

No records should be disposed of without the written approval of argenx BVBA.

For trials conducted outside the US under a US investigational new drug (IND), the principal investigator must comply with US FDA IND regulations and with those of the relevant national and local health authorities.

11.2. Direct Access to Source Data/Documents

The sponsor or designee and auditor may access patient records for the purpose of monitoring this trial, auditing, and managing progress details. The investigator must be fully aware that the sponsor or designee and auditor can inspect or verify documents to verify patient chart and eCRF records. Such information must be kept confidential and must have locked facilities that allow for this. The investigator will prepare and maintain adequate and accurate source documents to record all observations and other pertinent data for each patient enrolled into the trial.

The investigator is responsible for maintaining source documents. These will be made available for inspection by the Clinical Trial Monitor at each monitoring visit. The investigator must submit a completed eCRF for each patient who receives efgartigimod, regardless of duration. All supportive documentation submitted with the eCRF, such as laboratory or hospital records, should be clearly identified with the trial and patient number. Any personal information, including patient name, should be removed or rendered illegible to preserve individual confidentiality.

11.3. Investigator Information

11.3.1. Investigator Obligations

The investigator is responsible for ensuring that all trial site personnel, including sub-investigators, adhere to all applicable regulations and guidelines, including local laws and regulations, regarding the trial, both during and after trial completion. The investigator is responsible for informing the IRB/IEC of the progress of the trial and for obtaining annual IRB/IEC renewal. The investigator is responsible for informing the IRB/IEC of completion of the trial and will provide the IRB/IEC with a summary of the results of the trial.

11.3.2. Protocol Signatures

After reading the protocol, each investigator will sign the protocol signature page and send a copy of the signed page to the sponsor or representative. By signing the protocol, the investigator confirms in writing that he/she has read, understands, and will strictly adhere to the trial protocol and will conduct the trial in accordance with ICH Tripartite Guidelines for GCP and applicable regulatory requirements. The trial will not be able to start at any site where the investigator has not signed the protocol.

11.3.3. Publication Policy

All information regarding efgartigimod supplied by the sponsor to the investigator and all data generated as a result of this trial, are considered confidential and remain the sole property of the sponsor. The results of the trial will be reported in a CTR.

The CTR written in accordance with the ICH E3 Guideline, will be submitted in accordance with local regulations.

Any manuscript, abstract or other publication or presentation of results or information arising in connection with the trial must be prepared in conjunction with the sponsor and must be submitted to the sponsor for review and comment prior to submission for publication or presentation. Trial patient identifiers will not be used in publication of results.

Authorship will be granted based on scientific input, recruitment efforts, and will be granted upon decision of a publication committee. This committee will include among others the coordinating investigator and the sponsor.

The sponsor will register and/or disclose the existence of and the results of clinical trials as required by law.

11.3.4. Financing and Insurance

The sponsor will fund the trial as outlined in the Clinical Trial Agreement.

The sponsor will obtain adequate global/local insurance for the trial participants including the trial patients for the required duration of time.

The sponsor maintains an insurance coverage for this trial in accordance with the laws and regulations of the countries in which the trial is performed. Liability and insurance provisions for this trial are specified in the investigator's contract. The terms and conditions will apply as specified in the policy document.

13. APPENDICES

APPENDIX 1: Myasthenia Gravis Activities of Daily Living

Grade	0	1	2	3	Score
Talking	Normal	Intermittent slurring or nasal speech	Constant slurring or nasal, but can be understood	Difficult to understand speech	
Chewing	Normal	Fatigue with solid food	Fatigue with soft food	Gastric tube	
Swallowing	Normal	Rare episode of choking	Frequent choking necessitating changes in diet	Gastric tube	
Breathing	Normal	Shortness of breath with exertion	Shortness of breath at rest	Ventilator dependence	
Impairment of ability to brush teeth or comb hair	None	Extra effort, but no rest periods needed	Rest periods needed	Cannot do one of these functions	
Impairment of ability to arise from a chair	None	Mild, sometimes uses arms	Moderate, always uses arms	Severe, requires assistance	
Double vision	None	Occurs, but not daily	Daily, but not constant	Constant	
Eyelid droop	None	Occurs, but not daily	Daily, but not constant	Constant	
					Total score _____

Source: website MGFA, MG-ADL^{19,20}

APPENDIX 2: Quantitative Myasthenia Gravis Score

Quantitative MG score					
Test item	None	Mild	Moderate	Severe	Score
Grade	0	1	2	3	
Double vision on lateral gaze right or left (circle one), seconds	61	11-60	1-10	Spontaneous	---
Ptosis (upward gaze), seconds	61	11-60	1-10	Spontaneous	---
Facial muscles	Normal lid closure	Complete, weak, some resistance	Complete, without resistance	Incomplete	---
Swallowing 4 oz. water (1/2 cup)	Normal	Minimal coughing or throat clearing	Severe coughing /choking or nasal regurgitation	Cannot swallow (if not attempted)	---
Speech after counting aloud from 1 to 50 (onset of dysarthria)	None at 50	Dysarthria at 30-49	Dysarthria at 10-29	Dysarthria at 9	---
Right arm outstretched (90 degree sitting), seconds	240	90-239	10-89	0-9	---
Left arm outstretched (90 degree sitting), seconds	240	90-239	10-89	0-9	---
Vital capacity, % predicted	≥80	65-79	50-64	<50	---
Right-hand grip, kgW					
Men	≥45	15-44	5-14	0-4	---
Women	≥35	10-29	5-9	0-4	---
Left-hand grip, kgW					
Men	≥35	15-34	5-14	0-4	---
Women	≥25	10-24	5-9	0-4	---
Head lifted (45 degree supine), seconds	120	30-119	1-29	0	---
Right leg outstretched (45 degree supine), seconds	100	31-99	1-30	0	---
Left leg outstretched (45 degree supine), seconds	100	31-99	1-30	0	---
Total QMG score (range, 0-39)					

Source: website MGFA, Quantitative MG score^{21,22}

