4.3. Selection of Trial Population

4.3.1. Inclusion Criteria

Patients will roll over in this trial only if they meet **all** of the following criteria:

1. Patients with the ability to understand the requirements of the trial, provide written informed consent, and can comply with the trial protocol procedures.
2. Patients who participated in trial ARGX-113-1704 and are eligible for roll over, ie:
 - Patients who reached EoS at day 182 in trial ARGX-113-1704.
 - Patients who need (re-)treatment in trial ARGX-113-1704 but cannot complete a Treatment Cycle within the time frame of that trial may immediately roll over into this trial to receive treatment with efgartigimod.
 - Patients who discontinued early from randomized treatment for other reasons than pregnancy, rescue therapy or an (S)AE in trial ARGX-113-1704 may be offered the option to roll over into this trial.
 - Patients who had a temporary interruption from randomized treatment in trial ARGX-113-1704 may be offered the option to roll over into this trial.
3. Patients are required to be on a stable dose of their MG treatment (SoC) prior to SEB. The SoC is limited to AChE inhibitors, steroids and NSIDs (eg, azathioprine, methotrexate, cyclosporine, tacrolimus, mycophenolate mofetil, and cyclophosphamide).

Note: AChE inhibitors must be withheld for at least 12 hours consistent with the revised manual for the QMG test as recommended by the Myasthenia Gravis Foundation of America (MGFA), before the QMG assessment.

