7.1.2. Quantitative Myasthenia Gravis

The QMG quantifies disease severity based on impairments of body functions and structures as defined by the International Classification of Functioning, Disability and Health.¹⁸

The QMG consists of 13 items (Appendix 2) that assess ocular, bulbar, and limb function. Out of the 13 items, 6 are timed tests of endurance measured in seconds. Each item has a possible score from 0-3. The total possible score is 39, where higher total scores indicate more severe impairments. It is based on quantitative testing of specific muscle groups to assess limb function. It requires minimal equipment such as spirometer, mouthpieces that fit the spirometer, nose clips, stopwatch, cups and water for swallowing tests, goniometer, dynamometer, and is based on the trained rater's examination. The scoring of QMG should be performed by a trained evaluator.

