4. EFFICACY, PHARMACODYNAMICS AND ANTI-DRUG ANTIBODIES ANALYSES

4.1 EFFICACY

4.1.1 *Available data*

Efficacy will be assessed using MG-ADL (part A and B) and QMG (part A only).

4.1.2 *Endpoints and derivation rules*

1) Actual values and change from baseline and CnB in total MG-ADL score will be analysed descriptively and categorically.

Categories to be used for actual values in MG-ADL total score: 0, 1, 2, 3, 4, 5-7, 8-9, 10-12, 13-16, 17-20 and 21-24.

Categories to be used for changes from baseline and CnB in MG-ADL total score: >0, 0, -1, -2, -3, -4, -5, -6, -7, -8, -9, -10, <-10. Number of patients, percentages and cumulative percentages will be shown.

In addition to the planned timepoints, following timepoints will be shown for each cycle:

- Maximum drop from baseline and CnB in MG-ADL
- Minimum MG-ADL score: descriptively and categorically

Missing data will not be considered.

Analysis will be done on AChR-Ab seropositive patients, AChR-Ab seronegative patients and overall.

2) Actual values and change from baseline and CnB in total QMG score will be described descriptively and categorically as for the MG-ADL score. For the categorization of the QMG total score actual values a category of >24 will be added.

4.1.3 *Statistical analysis*

Summary statistics will be provided in terms of absolute values and changes from baseline (overall) and CnB (for each cycle) for MG-ADL and QMG total scores in AChR-Ab seropositive patients, AChR-Ab seronegative patients and the overall safety population.

Absolute values and changes from baseline (overall) and CnB (for each cycle) in MG-ADL and QMG total scores will also be categorized, including the number of patients within each category, the percentage, and the cumulative percentage.

See section 8 for a list of tables and listings.

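### As printed, Appendix 2 gives no QMG grade for a woman's right-hand grip of 30-34 kgW, so the item and the total are ambiguous by 1 point for such a reading

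*Protocol*

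**What the plan says.** Protocol 7.1.2 sends the reader to Appendix 2 for the 13 QMG items and states: "Each item has a possible score from 0-3. The total possible score is 39". Every reading therefore needs a grade.

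Appendix 2 gives four grip rows in kgW, each listing grades 0, 1, 2 and 3 in that order:

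- Right hand, men: "Men ≥45 15-44 5-14 0-4"
- Right hand, women: "Women ≥35 10-29 5-9 0-4"
- Left hand, men: "Men ≥35 15-34 5-14 0-4"
- Left hand, women: "Women ≥25 10-24 5-9 0-4"

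The table is credited as follows: "Source: website MGFA, Quantitative MG score". The protocol also mentions a QMG manual in Section 4.3.1, the synopsis and a footnote to Table 1, but only to support withholding acetylcholinesterase inhibitors before the test ("consistent with the revised manual for the QMG test as recommended by the Myasthenia Gravis Foundation of America"). Neither source's grip limits appear anywhere else in the two documents.

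Protocol 3.3 makes change in total QMG from the first and from the corresponding treatment period baseline a tertiary endpoint for Part A, in the seropositive and in the overall population. SAP 4.1.2 sets the analysis: "Actual values and change from baseline and CnB in total QMG score will be described descriptively and categorically as for the MG-ADL score". It adds one actual-value category above 24 for the QMG.

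**The concern.** The women's right-hand row stops grade 1 at 29 kgW and starts grade 0 at 35 kgW. The table does not show which limit is wrong. Lowering the grade 0 limit to 30 scores the gap as 0; raising the grade 1 limit to 34 scores it as 1. Both give a complete row, and they differ by 1 point.

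The SAP's change categories are 1 point wide from 0 to -10, so 1 point is enough to move a patient between them. A woman's QMG change can be affected in two ways. Either exactly one of her two readings lies in 30-34, so that her change depends on which rule is used, or the gap is filled by different rules at her two visits. As printed, the score of a named endpoint cannot be reproduced from the protocol for these readings.

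**Working it through.** **Inputs.** The four grip rows and the vital capacity row come from Protocol Appendix 2, the item count and range from Protocol 7.1.2, and the categories from SAP 4.1.2.

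**The plan's own figure.** Maximum total = 13 items x 3 = 39, which agrees with the protocol. The problem is coverage of the item, not the total.

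**Step 1: coverage.** Each whole-number reading was compared with the printed bands. The step is the grade 0 minimum minus the grade 1 maximum; a step of 1 means the bands meet.

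| Row | Step | Ungraded readings |
|---|---|---|
| Right, men | 45 - 44 = 1 | none |
| Right, women | 35 - 29 = 6 | 30, 31, 32, 33, 34 |
| Left, men | 35 - 34 = 1 | none |
| Left, women | 25 - 24 = 1 | none |

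No row has overlapping bands. The vital capacity row is also complete in whole numbers.

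**Step 2: effect on one visit.** Rule A grades 30-34 as 0; rule B grades it as 1. The difference is 1 - 0 = 1 point, on 1 of 13 items and out of 39 points.

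**Step 3: effect on a change, with one rule throughout.** Item change = later grade minus baseline grade.

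| Grip, baseline to later (kgW) | Rule A | Rule B |
|---|---|---|
| 28 to 32 | 0 - 1 = -1 | 1 - 1 = 0 |
| 32 to 36 | 0 - 0 = 0 | 0 - 1 = -1 |
| 33 to 28 | 1 - 0 = +1 | 1 - 1 = 0 |
| 31 to 33 | 0 - 0 = 0 | 1 - 1 = 0 |
| 25 to 36 | 0 - 1 = -1 | 0 - 1 = -1 |

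Over all 61 x 61 pairs of readings from 0 to 60 kgW, the rules give different changes if and only if exactly one reading lies in 30-34, and then always by 1 point.

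**Step 4: effect on a change, with different rules at the two visits.** For 31 to 33 kgW, A then B gives 1 - 0 = +1, and B then A gives 0 - 1 = -1. Either is spurious, and the possible results span 2 points.

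**Step 5: SAP change categories** (>0; 0; -1 to -10 singly; <-10). One further point of fall changes the category when the total change is +1, 0, or -1 to -10: 1 + 1 + 10 = 12 values. It has no effect between +2 and +1, or once the change is already below -10.

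**Step 6: SAP actual-value categories** (0, 1, 2, 3, 4, 5-7, 8-9, 10-12, 13-16, 17-20, 21-24, >24). A 1-point step crosses a limit at 0/1, 1/2, 2/3, 3/4, 4/5, 7/8, 9/10, 12/13, 16/17, 20/21 and 24/25: 11 of the 39 steps.

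Steps 5 and 6 count possible values, not patients. The documents give no grip data, so no frequency or effect on a mean can be computed.

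**The case against.** **A misread digit.** The text was extracted from a PDF, and the finding rests on one number in one cell. This cannot be excluded. However, the row has four cells in order, and its grade 2 band, grade 3 band and grade 1 lower limit match the women's left-hand row. It does not look broken, and the first step of the fix is to look at the page.

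**Shorthand elsewhere in the table.** Read literally, several timed items give a single value for grade 0 (such as 61, 240, 120 or 100 seconds), and the worst speech grade is a single count of 9. Symbols may have been lost, or trained raters may be expected to complete the table. Those cells have one natural reading, though; 30-34 kgW has two.

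**Trained raters and outside sources.** Protocol 7.1.2 requires a trained evaluator, and the MGFA source, the manual or the eCRF may already have fixed the cut-off. That may be so, but the documents do not show it. What is established is a defect in the printed table, not an error in scored data.

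**The same rater over time.** Protocol 7.1 prefers one evaluator per patient, and Protocol 9.2 asks for every effort to keep the baseline assessor. This makes mixed rules (step 4) less likely. It does not help when only one of the two readings lies in the gap (step 3).

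**Weight and timing.** The endpoint is tertiary, descriptive and Part A only. The final-analysis SAP is dated 20 September 2022, so correcting the table may come after most scoring was done. This limits the importance of the point and makes the query on the rule actually applied more useful than the edit.

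**Conclusion.** The concern holds at minor weight. At least one limit in the women's right-hand grip row must be wrong as printed, since 5 whole-number readings in 1 of 4 grip rows have no grade. The ambiguity is 1 point per affected visit. It is at most 1 point in a change score under a single rule, with a span from -1 to +1 if rules were mixed.

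The primary safety endpoint is untouched, and the Part A re-treatment and treatment-failure rules in Protocol 4.1 use MG-ADL. The conclusion assumes that the extracted row matches the original page and that no rule in the rater manual or eCRF, neither of which is shown, already settles it. The number of women with a reading of 30-34 kgW is unknown and could be zero.

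**What to change.** 1. Check the row on the original protocol page, then against the MGFA source and the revised QMG manual that the protocol cites.
2. Change whichever limit proves wrong so that grades 0 and 1 meet. If the source has the same gap, keep the published instrument and state a scoring rule for 30-34 kgW.
3. Ask which cut-off the raters and the eCRF used, and whether it was the same at all sites and visits.
4. If raw kgW values were captured, re-derive the item and the total under that single rule. If not, document the rule applied in the SAP or the clinical trial report.

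The cost is one table cell and one query. Step 4 depends on raw grip values having been recorded, which the documents do not say: the QMG listing in SAP 8.2 names only the total score and derived variables.
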